I agree to have control over all clinical supplies and the investigational product provided by CathVision. I further agree not to originate or use the name of CathVision ApS and/or ECGenius® System, or any of its employees, in any publicity, news release or other public announcements, written or oral, whether to the public, press or otherwise, relating to this protocol, to any amendment hereto, or the performance hereunder, without the prior written consent of CathVision ApS.

I herewith declare that I agree with the protocol described in detail in this document and agree to conduct the study in accordance with the protocol and compliance with Good Clinical Practice and all applicable regulatory requirements.

INVESTIGATOR SIGNATURE

Signature	Location	Date
Name:		dd-Mmm-yyyy
Title:		

PROTOCOL SYNOPSIS

Title	The automated calculation of AF cycle length and complexity using a novel EP recording system (CathVision ECGenius® System).
Investigational Device	CathVision ECGenius® System
Objective	Collect electrophysiological data during atrial fibrillation (AF) ablation procedures to assess the performance of a Signal Complexity Visualization algorithm, designed to be integrated into the CathVision ECGenius® System at a later stage.
Study Design	
A prospective, single-center, feasibility study using the CathVision ECGenius® system and a Signal Complexity Visualization Algorithm during radiofrequency (RF) ablation procedures to treat persistent AF.
 
Subjects with persistent AF who are indicated to undergo a routine-practice RF ablation may be enrolled in the Study. Intracardiac signals will be passively recorded using the investigational CathVision ECGenius® System in parallel with the commercial (CE Approved) EP recording system used as standard of care at the investigational site. The investigational device will not be used for direct clinical care decisions or therapy.
 
The validation of the Signal Complexity Visualization Algorithm will be performed offline and retrospectively.

Sample Size	A minimum of 15 and up to 30 subjects may be enrolled in this study
Investigational Site	OLV Cardiovascular Centre, Aalst, Belgium
Study Duration / Follow-up Period	
Study enrollment is planned from October 2022 to December 2022.
 
Subjects will be followed until discharged from the hospital. There is no additional study follow-up planned.

Primary Endpoint	Assessment of the performance of a Signal Complexity Visualization Algorithm for analyzing AF response to ablation, evaluated as the technical success of the CathVision ECGenius® System to collect and record intracardiac signals during routine EP procedures.
Safety Endpoint	Evaluation of adverse events and/or device deficiencies reported with the use of the CathVision ECGenius® System during the procedure until discharge.

Enrollment Criteria	
Inclusion Criteria Eligible subjects must meet all of the following inclusion criteria:
 
1. Subjects undergoing RF ablation indicated by the investigator for the treatment of persistent atrial fibrillation.2. At least 21 years of age.3. Able and willing to provide written informed consent prior to any clinical investigation related procedure. 
Exclusion Criteria Eligible subjects must not meet any of the following exclusion criteria:
 
1. Current participation in another investigational drug or device study that interferes with this study.2. Presence of other anatomic or comorbid conditions, or other medical, social, or psychological conditions that, in the investigator's opinion, could limit the subject's ability to participate in the clinical investigation or to comply with follow-up requirements, or impact the scientific soundness of the clinical investigation results.3. Life expectancy less than 12 month, in the opinion of the Investigator.4. Subjects who, in the opinion of the investigator, are not candidates for this study.5. Subjects who, in the opinion of the investigator, are considered part of any vulnerable population.
----------------------------	---

TABLE OF CONTENTS

Contents

ADMINISTRATIVE INFORMATION	2
Contacts:	2
Amendment History:.....	2
Sponsor Protocol Approval.....	3
Investigator's Agreement.....	4
1. INTRODUCTION.....	11
1.1 Cardiac Electrophysiology.....	11
1.2 Intracardiac Electrophysiology Signals	11
1.3 Rationale for this Clinical Investigation	11
2. DEVICE DESCRIPTION.....	12
2.1 Signal Processing Overview	12
2.2 Intended Purpose.....	13
3. RISK-BENEFIT ANALYSIS	14
4. INVESTIGATIONAL PLAN.....	14
4.1 Study Objectives	14
4.2 Study Design.....	14
4.3 Study Duration	15
4.4 Subject Population	15
4.4.1 Inclusion Criteria	15
4.4.2 Exclusion Criteria	15
4.4.3 Point of Enrollment.....	16
4.5 Study Endpoints	16
4.5.1 Primary Endpoint	16
4.5.2 Safety Endpoint.....	16
4.6 Study Procedures	16

1. INTRODUCTION

1.1 CARDIAC ELECTROPHYSIOLOGY

Of the total worldwide population, 1% and 2% of rural and urban areas suffer from cardiac arrhythmia, respectively. Approximately 15% of patients do not respond to drug treatment and need a device-based interventional treatment. As a result, there is a large and growing need for cardiac arrhythmia ablation. Today, however, precise identification of the mechanism of the arrhythmia and subsequent successful ablation treatment is challenging for physicians. The three most prevalent arrhythmias (“complex arrhythmias”) for catheter ablation are atrial fibrillation, atrial tachycardia, and ventricular tachycardia.¹

1.2 INTRACARDIAC ELECTROPHYSIOLOGY SIGNALS

Cardiac electrograms are generated by the potential (voltage) differences recorded at two recording electrodes during the cardiac cycle. All clinical electrogram recordings are differential recordings from one source that is connected to the anodal (positive) input of the recording amplifier and a second source that is connected to the cathodal (negative) input. Unipolar recordings are obtained by positioning the exploring electrode in the heart and the second electrode (referred to as an indifferent electrode) distant (theoretically an infinite distance) from the heart such that it has little or no cardiac signal.

Bipolar recordings are obtained by connecting two nearby electrodes that are exploring the area of interest to the recording amplifier. The recorded signal is the potential difference from the positive input to the negative input. Because a signal from a far-field source will present a common potential to the two electrodes, it is largely subtracted out, leaving the local signal. In a homogeneous sheet of tissue, the initial peak of the bipolar signal coincides with depolarization beneath the recording electrode².

Cardiac arrhythmias can be mapped by measuring the cardiac electrograms at relevant anatomical locations, such as within the left atrium for atrial fibrillation.

1.3 RATIONALE FOR THIS CLINICAL INVESTIGATION

Paroxysmal atrial fibrillation (AF) is characterized by episodes of chaotic atrial activation that are shorter than seven days in length and self-terminate without interventions such as drug therapy or electrical cardioversion.¹ For paroxysmal AF patients who do not respond to anti-arrhythmic drug therapy, a pulmonary vein isolation (PVI) may be indicated for symptom relief.¹

Persistent AF is diagnosed when patients have episodes of AF lasting longer than seven days or require intervention to terminate the arrhythmia.¹ The persistent AF patient group is highly heterogeneous and ranges from patients with only short episodes of AF who are very symptomatic and seek medical attention often leading to cardioversion; to patients who have been in AF for several years under the care of a primary care physician. Whilst the guidelines for ablation of patients in paroxysmal AF clearly indicate PVI employing radiofrequency (RF) guided by a 3D mapping system, or cryo or laser balloon ablation, it is widely thought that PVI alone is not an adequate treatment for many persistent AF patients.³ Ablation strategies in addition to PVI range from: targeting areas of low amplitude electrograms, which may indicate areas of disease;⁴ mapping and ablation of areas exhibiting complex fractionated waveforms;⁵ mapping and ablation of areas

displaying rotating activation;⁶ mapping and ablation of unipolar electrograms with a qS morphology revealing a focal source driver;⁷ linear ablation strategies to create lines of block between anatomical structures;⁸ or even combinations of these approaches.⁸

Whilst many of these approaches have shown promise in improving outcomes for persistent AF patients, particularly when compared to PVI alone, the operator often has very little indication of the impact the ablation strategy is having on the underlying rhythm during the procedure. Signal features derived from the atrial electrogram during AF may be used to describe the fibrillation rhythm. As an example, the cycle length of AF (AFCL) is indicative of atrial refractoriness and can be calculated from atrial electrograms using signal processing techniques. Studies using off-line, post-procedure, retrospective processing techniques have shown that ablation may lead to a lengthening of AFCL as a precursor to reversion to sinus rhythm.⁹ Indeed, such signal features may be derived from both the time (cycle length) and frequency (dominant frequency) domains. Analysis in the frequency domain has previously been used to create an index of the complexity of AF. Spectral analysis of the signal using fast Fourier transform techniques identifies the power of the dominant frequency and compares this to the total power of the signal. The greater the power of the dominant frequency, the less complex the signal.¹⁰

CathVision has developed an algorithm that derives features from the ECG and intracardiac electrogram signals and returns analytical information in the form of signal complexity and cycle length to the operator. In this way, the operator will be able to assess the impact of their ablation procedure.

2. DEVICE DESCRIPTION

The CathVision ECGenius® System is an investigational electrophysiology (EP) recording system to be used in EP procedures as a tool to monitor, display, and record signals of the heart and cardiac arrhythmias. The investigational device ECGenius® System includes the following items:

- Cube® EP amplifier (EPAMP)
- Pin box cable assembly for connection of catheters
- Surface ECG cable
- Data cable to host computer
- Recording system software (RECORDER SW)
- Host computer (Cube PC) and monitors

[figure not shown]
The Signal Complexity Visualization Algorithm will be used in this study to assess AF cycle length and complexity after the procedure, in an offline and retrospective manner.

Additional information regarding the device and its components, including all pre-clinical and clinical test results, can be found in the Investigator's Brochure or in the Instructions for Use.

2.1 SIGNAL PROCESSING OVERVIEW

The main hardware of the ECGenius® System is the amplifier or Cube® EPAMP, which acquires signals from third-party catheters and sensors connected to the patient. It then sends the signals to the ECGenius® PC, which has a software program called the RECORDER SW that visualizes the

signals to the user and provides the users a way to interactively analyze them. The following figure illustrates this signal pathway.

There are no parts of the medical device that may come into contact with the subject's body or body fluids. There are no medicinal products, human or animal tissues or their derivatives, or other biologically active substances used in the device.

Each manufacturing lot of investigational device part is assigned a unique lot number that is printed on the device package labeling, providing a means of traceability. A device accountability log will be used to track the use of devices in the study. The lot number will be recorded in each case report form.

The CathVision ECGenius® System will be labeled "for investigational use only."

2.2 INTENDED PURPOSE

The ECGenius System is an electrophysiology measurement system used to acquire, filter, digitize, amplify, display, and record clinical data obtained during electrophysiological studies and related procedures. The system is compatible with a 3rd-party stimulator, intended to be used for diagnostic cardiac stimulation during electrophysiological testing of the heart. The ECGenius is not intended for use with flammable gases or liquids. No part of it is sterile or sterilizable and the device is protected from ingress of fluids (IPX1).

The ECGenius is designed for use in air-conditioned hospital EP laboratories and operating rooms equipped for advanced cardiac resuscitation.

The intended users are licensed healthcare professionals (e.g. electrophysiologists), technicians and nurses working in EP laboratories and operating rooms. Typically, a technician operates the ECGenius System and a practitioner interprets the data. The nurses play a secondary role as they assist the practitioner and technician.

The intended patients are adult patients diagnosed with cardiac arrhythmia, including patients with supraventricular tachycardia and ventricular tachycardia.

3. RISK-BENEFIT ANALYSIS

The clinical investigation has been designed to involve as little pain, discomfort, fear, and any other foreseeable risk as possible for subjects. There are no known risks to the potentially enrolled subjects specifically associated with the use of the ECGenius® System, since this investigational device will passively record EP signals in parallel to a commercial and standard of care EP recording system, thus not impacting any clinical procedures.

Potential study risks include product failures similar to commercially available EP recording systems, with a similar likelihood of occurrence.

Risks associated with cardiac electrophysiology procedures include events reported in the literature related to catheter procedures, identified in the risk and hazard analyses, and associated with percutaneous interventions. A list of anticipated adverse events are defined in Section 6.5. Each adverse event and/or device effect will be evaluated in detail as described in Section 6 of this Clinical Investigation Plan (CIP).

The study is designed for parallel data collection during an electrophysiology study. The investigator diagnostic decisions will be guided by an approved EP recording system as per institution standard of care. Due to the protocol design and noninvasive nature of the tested medical device the rate of expected occurrence of SAEs or SADEs related to the use of the investigational device is low.

CathVision personnel will be responsible for the installation of the investigational device. During the study, the device will be operated by study trained site personnel.

As the treatment will be guided by an approved EP recording system, the reduction in symptomatic arrhythmia will be similar to the benefit of currently available EP recording systems.

4. INVESTIGATIONAL PLAN

4.1 STUDY OBJECTIVES

The primary objective of the study is to validate a Signal Complexity Visualization algorithm with a novel EP recording system (CathVision ECGenius® System) for the assessment of measurable changes to rhythm during persistent AF ablation procedures.

The safety of the CathVision ECGenius® System will be evaluated through adverse events and/or device deficiencies reported during the procedure until discharge.

4.2 STUDY DESIGN

This is a prospective, single-center, feasibility study using the CathVision ECGenius® system and a Signal Complexity Visualization Algorithm during radiofrequency (RF) ablation procedures to treat persistent AF.

Subjects with persistent atrial fibrillation who are indicated to undergo an RF ablation may be enrolled in the Study. Intracardiac signals will be passively recorded using the investigational

ECGenius® System in parallel with the commercial (CE Approved) CardioLab, GE EP recording system. The investigational device will not be used for direct clinical care decisions or therapy. The validation of the signal complexity algorithm will be performed offline. A summary of the schedules of evaluations and visits can be found in section 4.7.1.

4.3 STUDY DURATION

Study enrollment is planned for 1-3 months between October and December 2022.

Subjects will be followed until discharged from the hospital, regardless of the duration of hospitalization. After the EP procedure, the estimated number of days of hospitalization is 1-2. There is no additional study follow-up planned.

4.4 SUBJECT POPULATION

A minimum of 15 and up to 30 subjects will be enrolled in the study at the investigational site.

Eligible subjects must meet the inclusion and exclusion criteria described in Sections 4.4.1 and 4.4.2 to be enrolled in the study and undergo an EP procedure using the CathVision ECGenius® System in parallel to the commercial EP system.

4.4.1 INCLUSION CRITERIA

Subjects must meet all of the following inclusion criteria to be included in the study:

1. Subjects undergoing ablation indicated by investigator for the treatment of persistent atrial fibrillation.
2. At least 21 years of age.
3. Able and willing to provide written informed consent prior to any clinical investigation related procedure.

4.4.2 EXCLUSION CRITERIA

Subjects will not be eligible for the study if any of the following exclusion criteria are met:

1. Current participation in another investigational drug or device study that interferes with this study.
2. Presence of other anatomic or comorbid conditions, or other medical, social, or psychological conditions that, in the investigator's opinion, could limit the subject's ability to participate in the clinical investigation or to comply with follow-up requirements, or impact the scientific soundness of the clinical investigation results.
3. Life expectancy less than 12 month, in the opinion of the Investigator.
4. Subjects who, in the opinion of the investigator, are not candidates for this study.
5. Subjects who, in the opinion of the investigator, are considered part of any vulnerable population.

4.4.3 POINT OF ENROLLMENT

A subject is considered enrolled in the clinical investigation from the moment the patient provides written informed consent, has been confirmed to meet all inclusion criteria and none of the exclusion criteria, and has undergone initiation of the treatment procedure.

4.5 STUDY ENDPOINTS

4.5.1 PRIMARY ENDPOINT

The Primary endpoint of the study will be evaluated as the technical success* of CathVision ECGenius® System to collect and record intracardiac signals during routine EP procedures. Specifically:

- To extract and quantify atrial fibrillation electrogram features from the CS catheter.
- To visualize changes and label events during the procedure in relation to RF ablation delivery.

*The Signal Complexity Visualization Algorithm relies on local activation time (LAT) detection. An error in LAT annotation will produce a "no result". Technical success is defined as data of sufficient quality (low noise, detectability of LATs) for the algorithm to produce a result.

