7. STATISTICAL METHODS

7.1 SAMPLE SIZE CALCULATION

This prospective, single center, feasibility study is intended to collect data from patients in AF rhythm in order to test the feasibility of displaying changes in signal complexity. As a result, no formal statistical hypothesis was applied to derive the sample size. The selection of the sample size was made using a non-probability, purposive method.

If subjects receive treatment without meeting all the CIP-required conditions, they are counted in the Intent-to-Treat (ITT) population, they will not be deregistered from the clinical investigation, and they should complete all follow-up requirements. These subjects are considered CIP deviations, and are excluded from the sample size calculation and endpoint analysis. For a detailed description of the statistical analysis with respect to the enrolled population and deviations, refer to the Statistical Analysis Plan (SAP).

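### The technical-success rule in 4.5.1 is not tied to the endpoint's second component, so one result before the first RF application is enough to count as success

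*Combined protocol and SAP*

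**What the plan says.** Section 4.5.1 makes the primary endpoint the technical success of the system in recording intracardiac signals, and then lists two specific components. The first is to extract and quantify AF electrogram features from the CS catheter. The second is "To visualize changes and label events during the procedure in relation to RF ablation delivery".

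A footnote supplies the only pass rule: "Technical success is defined as data of sufficient quality (low noise, detectability of LATs) for the algorithm to produce a result". It adds that an error in annotating local activation times (LATs) leads to no result.

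The statements of purpose concern change or response:

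- Section 4.1: the algorithm is to be validated "for the assessment of measurable changes to rhythm during persistent AF ablation procedures".
- Synopsis: the algorithm is "for analyzing AF response to ablation, evaluated as the technical success of the CathVision ECGenius® System to collect and record intracardiac signals".
- Section 7.1: data are collected to "test the feasibility of displaying changes in signal complexity".

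Section 4.5.2 leaves the detailed endpoint methods to the SAP, and 7.1 and 7.2 also refer to it. The text available for this review contains no endpoint-specific analysis beyond the general descriptive statistics of 7.2.

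**The concern.** Displaying a change within a subject takes at least two results in AF: one before RF energy is first delivered and one after delivery has begun. The pass rule asks for one result and does not say when. A subject whose CS signal can be annotated while catheters are being placed, but not once RF starts, would meet it. The reported rate could then be high with few evaluable before-and-after pairs behind it, and a reader could take it as evidence that change can be displayed. The point concerns when results are available. It does not concern whether they are accurate.

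Rhythm matters as well. Section 1.3 cites work in which "ablation may lead to a lengthening of AFCL as a precursor to reversion to sinus rhythm". Once AF has ended, AF features cannot be obtained. Any rule that requires a later result must therefore separate the end of AF from a technical failure to annotate, and 4.5.1 does not make that distinction.

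**Working it through.** **Plan's own figure.** There is none to reproduce. Section 7.1 states that no formal hypothesis was used. The sample is 15 to 30 subjects (4.4), with no target rate, alpha or power.

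**The texts side by side.**

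| Question | What the protocol gives |
|---|---|
| When must a result exist? | Not stated in 4.5.1 |
| How many results, or what share of the recording? | Not stated in 4.5.1 |
| Per segment, per recording or per subject? | Not stated in 4.5.1 |
| Criterion for the second component? | None in 4.5.1 |
| Required recordings before, during and after RF? | None listed in 4.7.3, which describes parallel recording during catheter manipulation or diagnostic tests |
| Is no result a failure or missing data? | Not stated; 7.2 says only that missing data are not imputed |
| Must the subject be in AF at the procedure? | Not in 4.4.1, although 7.1 speaks of patients in AF rhythm |

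**How far the two rates can separate.** Let L be the number of subjects with a result at any time (the literal rule). Let P be the number with a result both before and after the start of RF. P cannot exceed L, and nothing in the rule limits L − P.

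*Illustration 1 (assumed yields).* Take n = 15, all in AF before RF. Fourteen give a result before RF, 8 of those also give one after RF starts, and the fifteenth gives none.

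- L/n = 14/15 = 93.3%
- P/n = 8/15 = 53.3%
- Difference = 6/15 = 40 percentage points

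If all 14 keep a result after RF starts, the two rates coincide.

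*Illustration 2 (assumed).* Every subject has a result before RF, and a share q also has one during or after RF. The exact 95% (Clopper-Pearson) limits for x of n are the 0.025 quantile of Beta(x, n − x + 1) and the 0.975 quantile of Beta(x + 1, n − x). At x = 0 the lower limit is 0, and at x = n the upper limit is 100%.

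| q | Paired, n = 15 (95% CI) | Paired, n = 30 (95% CI) |
|---|---|---|
| 1 | 15/15 (78.2–100%) | 30/30 (88.4–100%) |
| 0.8 | 12/15 (51.9–95.7%) | 24/30 (61.4–92.3%) |
| 0.6 | 9/15 (32.3–83.7%) | 18/30 (40.6–77.3%) |
| 0.4 | 6/15 (16.3–67.7%) | 12/30 (22.7–59.4%) |
| 0 | 0/15 (0–21.8%) | 0/30 (0–11.6%) |

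The literal rule reports the first row, 15/15 or 30/30, whatever q is.

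*Illustration 3 (assumed, phases independent).* With probability a of a result before RF and b after RF starts, the chance of any result is 1 − (1 − a)(1 − b) and the chance of a pair is ab. For a = 0.9 and b = 0.5 these are 1 − 0.1 × 0.5 = 0.95 and 0.45. For a = b = 0.9 they are 0.99 and 0.81.

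**The case against.** The strongest reply is that the footnote should be read together with the two components above it. Change in relation to RF is named as part of the primary endpoint, and a subject with output only before RF would not meet that component. Detailed methods are also deferred to the SAP, where windows and units of analysis would normally be set. A reader might infer from the footnote that the aim of displaying change is never measured. The documents do not support that: the second component names it, and an SAP may yet specify it. What stands is narrower. The only stated pass rule lacks timing, and the component that needs timing has no rule.

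A reader might also infer that the present rule penalises subjects whose AF terminates. It does not. Under the literal rule, a subject who produced a result before converting is already a success. Termination becomes a scoring problem only once a later result is required, so it is the revised rule that must deal with it.

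Nor do the documents suggest that the CS signal deteriorates once RF starts. The yields used here are assumptions. Section 6.6 would record loss of waveform or an interrupted recording as a device deficiency. However, those reports do not enter the success rate, and an intact recording on which LATs cannot be annotated need not appear among them.

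Finally, this is a feasibility study with no hypothesis or success threshold, and the device does not guide care. That limits the consequence. It does not remove the need for the rate to address the feasibility question that 7.1 poses.

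**Conclusion.** The point holds as a gap in the endpoint definition. Followed literally, 4.5.1 counts a subject with a result only before the first RF application as a success. The headline rate then need not show that change during ablation can be displayed.

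The size cannot be taken from the documents, which give no yield by procedure phase. The 93% and 53% figures show what the rule permits and are not a forecast. If every subject has a result before RF, the rule reports 100% while the share with an evaluable pair can lie anywhere from 0% to 100%. If results persist through ablation, the two rates agree and nothing is lost.

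The conclusion rests on two things: that the footnote is the operative rule, and that no SAP text outside the material available here already ties it to RF timing. If such text exists, 4.5.1 only needs to be aligned with it. The change should be made, but the study does not fail without it.

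**What to change.** In 4.5.1, and in matching terms in the SAP:

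- **Definition.** Among subjects in AF before the first RF application, per-subject technical success is at least one algorithm result in AF before the start of that application and at least one in AF after that start (during or after RF), on a recording with time-labelled RF applications.
- **AF termination.** Where AF ends, take the last AF segment after RF start and before termination as the later result. Do not count the absence of AF results after termination as technical failure. Timing the later window from the start of the first application also covers AF that ends during it.
- **Not evaluable for rhythm reasons.** Report separately the subjects not in AF before RF, and those with no AF segment after RF start. This is needed because 4.4.1 does not require AF at the procedure, so a sound recording in sinus rhythm could otherwise be scored as a technical failure.
- **Secondary figures.** Report the any-result rate, and the percentage of in-AF recording time that yields a result before and after RF start. The second figure guards against a single early result after RF start standing in for the whole ablation.
- **Precision.** Give the paired proportion with an exact confidence interval.

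The cost is protocol and SAP wording plus some offline tabulation. No new data are needed, provided that recording runs through RF delivery, as the second component presupposes. The downside is that the headline rate may be lower and its denominator smaller, in a study of only 15 to 30 subjects.
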